5.1.3 Subject Withdrawal Criteria

Procedures for handling subjects who are discontinued from the study are described in [Section 13.2](#).

6. TEST ARTICLES AND REGIMEN

6.1 Description

Test article name: CB-03-01 Cream, 1%
Active ingredient: Cortexolone 17 α -propionate (11-deoxy-hydrocortisone-17 α -propionate).
Other ingredients: Cetyl alcohol, glycerol monostearate, liquid paraffin, propylene glycol, tocopherol, sodium edetate, polysorbate 80, citric acid, purified water.

6.2 Instructions for Use and Application

Subjects will treat facial acne per protocol for nine months. Treatment of truncal acne will be discussed by the investigator and subject. If the subject desires, the truncal treatment area will be defined and agreed upon by the investigator and the subject. If the investigator and subject designate a treatment area for truncal acne, the subject must continue to treat this area per protocol for the duration of the study as detailed below. If the investigator and subject do not designate a treatment area for truncal acne at Baseline (Visit 4-LTF), one may be designated at subsequent visits (e.g., if acne worsens in the truncal area), but once treatment begins in such treatment area, the subject must continue to treat this area per protocol for the remainder of the study.

At the first visit, the subjects will be instructed to wash the area to be treated (entire face and trunk, if applicable) with mild soap and water and then dry the area gently. The study staff will then instruct the subject and parent/guardian (if applicable) on how to dispense the test article, how much of the test article to use, and where to apply the assigned test article. The first application of the test article should be applied in the office at Visit 4-LTF under supervision of the study staff after the treatment areas have been determined, except for those subjects with clear facial acne and no truncal acne. For subjects starting treatment at subsequent visits, the first dose of the test article will be applied at that visit under supervision of the study staff. Typically, for the face, about one (1) gram of the test article will be dispensed onto a fingertip and applied by gently dabbing small amounts of the test article on multiple regions of the face (e.g., forehead, nose, cheeks, chin). Using a fingertip, the test article will be spread to provide a thin, uniform layer of the test article **over the entire face**. In addition, if applicable, subjects who choose (with investigator's approval) to treat truncal acne should apply a thin uniform application of the test article to the

designated area(s) of the trunk (e.g., the shoulders, chest, and/or back). *Note: one (1) gram of cream will cover approximately a 8.5" x 11" (~22 cm x 28 cm) area.*

Subject and parent/guardian (if applicable) will also be provided with a Subject Instruction Sheet ([Appendix 1](#)) providing them with instructions on how to use and store the cream at home during the study period. Subjects and parents/guardians (if applicable) will be instructed to apply the test article to the whole face and trunk, if applicable, twice daily (morning and in the evening) for nine additional months. The subject should ideally allow at least eight hours between applications. All subjects should not wash the treated area for at least four hours following test article application and should not apply the test article within four hours prior to any study visit.

If a subject's acne is totally clear (i.e., IGA=0) on face and/or trunk at Visit 4-LTF, the subject will not apply the test article to the area(s) that is clear at home for the first month of the study and be reassessed at Visit 5 or earlier (after an unscheduled visit), if acne worsens (in either area) before Visit 5. If acne is totally clear on the face and the trunk has not been designated for treatment, the subject will not be dispensed the test article at Visit 4-LTF. For subjects whose acne is not totally clear (i.e., IGA>0) at Visit 4-LTF, the subject should apply the test article at home twice daily (morning and evening) as instructed by the study staff.

Over the course of the study, treatment on the face and/or trunk may be discontinued if/when acne clears (achieves an IGA of grade 0 or "minimal" grade 1) and re-instated if/when acne worsens (IGA \geq 2), according to the assessment of the investigator for each respective treatment area. If treatment is discontinued on face and trunk, all containers of the test article should be collected. If treatment is re-instated, sufficient test article will be dispensed to the subject; previously returned test article should NOT be re-dispensed, rather new containers of the test article will be dispensed as needed to the subject. Note: Subjects must be seen by the investigator via a scheduled or an unscheduled visit to change (i.e., restart or stop) the test article dosing on either treatment area (face and trunk). **If the subject feels that his/her acne has cleared, he/she should continue to apply the test article to the designated treatment area (face and/or trunk) as instructed by the investigator and call the investigator for an unscheduled visit. The subject should NOT change his/her dosing regimen until the investigator has documented acne clearance or significant worsening to support a change in the treatment.**

Subjects will be provided with a Subject Diary ([Appendix 2](#)) to record the dates and time of application, along with where the test article was applied. Subjects will be instructed to only apply the test article to the face and/or trunk as instructed by the investigator or designated study personnel. **Note: The dispensing, recording, and application of the test article by the subject may require adult supervision by the subject's parent/guardian.**

Subject and parent/guardian (if applicable) will be instructed to bring all the containers of cream (used and unused) and their completed diaries to each visit. The study staff will

weigh all the returned containers and will record the weights on the appropriate study medication accountability logs and case report forms (CRFs). Test articles that are returned should NOT be re-dispensed to the subject.

Subjects who are not compliant with applying the test article as instructed (determined from subject diaries and/or the weight of test article used) may be discontinued from the study.

6.3 Warnings, Precautions and Contraindications

The test article is for topical use only. Care should be taken to avoid contact with eyes and all mucous membranes. If contact with eyes occurs, rinse thoroughly with water.

Subjects with a known sensitivity to any of the ingredients in the test article should not participate in this study.

Should skin irritation or rash develop, subjects should discontinue use and contact the study site.

In case of accidental ingestion, subjects should contact the investigator immediately.

The effects of the test article in nursing mothers, pregnant women and their unborn children are unknown. WOCBP must not be pregnant or planning a pregnancy during the study period.

7. RANDOMIZATION ASSIGNMENT

There is no randomization assignment in this study. This is an open label, extension study in which all eligible subjects will be treated with CB-03-01 cream, 1% (i.e., the test article). About 600 subjects will be enrolled in this extension study to achieve at least 300 subjects on-study at 6 months and 100 subjects on-study at 12 months. These treatment durations include the 0 or 3 months of active treatment in the Phase 3 pivotal studies (CB-03-01/25 and CB-03-01/26). Enrollment will be competitive; upon enrollment of about 600 subjects in this study, the option for rollover will not be offered to other subjects in the Phase 3 pivotal studies (CB-03-01/15 and CB-03-01/26), even if those subjects are eligible. Enrolled subjects will be provided with labeled test article during the study period, as needed. Subject numbers will be carried over from the Phase 3 pivotal study [CB-03-01/25 or CB-03-01/26].

8. PRIOR AND CONCOMITANT THERAPIES

Current medications taken at the start of this study (Visit 4-LTF) will be recorded on the appropriate CRFs with the corresponding indication. The medications to be recorded include RX and OTC medications (except vitamins and dietary supplements not used to treat a medical condition). All medications taken on a regular basis should be recorded on

the Concomitant Medications form prior to commencing the use of the test article. Any medications that were used prior to the start of this study would have been recorded as part of the Phase 3 pivotal study [CB-03-01/25 or CB-03-01/26].

Therapies (medication and non-medication therapies) not restricted by the protocol may be used during the study for the treatment or prevention of disease or to maintain good health. Vitamins and mineral supplements are permitted at dosages considered by the investigator as reasonable for maintaining good health. Non-prohibited chronic therapies being used at Visit 4-LTF may be continued. Any changes in concomitant therapies during the study must be recorded on the Concomitant Therapy form. The reason for any change in concomitant therapies should be evaluated and, if appropriate, reported as, or in conjunction with, an AE.

8.1 Prohibited Medications or Therapies

During the study, subjects must not use the following products and/or procedures on the face or trunk:

- Any other investigational drug or use of any investigational device;
- Light treatments (including artificial tanning devices, blue light, laser, etc.), microdermabrasion, or chemical peels;
- Systemic spironolactone;
- Systemic retinoid therapy;
- All topical acne therapies not allowed per [Section 8.2](#) (e.g. retinoids, azelaic acid, dapsone, etc.).

Other chronic medications being used at the time of Visit 4-LTF can be continued at the discretion of the investigator. The reason for any changes in such concomitant medications and/or therapies should be reported as, or in conjunction with, an AE.

8.2 Allowed Medications or Therapies

All allowed concurrent acne medications and/or therapies must be given IN ADDITION to the test article and NOT IN PLACE of the test article.

During the study, if control of acne is insufficient, the following supplemental products and/or procedures may be used at the discretion of the investigator on the face or trunk:

- Hormonal contraceptives¹¹;
- Occasional use of systemic antibiotics for acne (not to exceed 12 continuous weeks) or for other medical needs;
- Systemic corticosteroids (for other medical needs);
- Occasional use of intralesional corticosteroid injections for nodular or cystic acne lesions (low dose, e.g., ~2 mg triamcinolone / cc) or for other medical needs;

¹¹ If hormonal contraception is initiated as concurrent acne therapy, the method of highly effective birth control used at Visit 4-LTF must be continued for at least two complete cycles (i.e., eight to twelve weeks).

- Occasional use of TOPICAL steroids or TOPICAL antibiotics for up to 10 continuous days (for other medical needs) within the treatment area (face and/or trunk);
- TOPICAL anti-acne cleansers (not leave-on products) that have benzoyl peroxide ($\leq 5\%$) OR salicylic acid ($\leq 2\%$) as their only active ingredient within the treatment area (face and/or trunk).

Acne Management: The intent of the study is to limit the use of other acne medications to facilitate the safety assessment of long-term use of the investigational test article over a one year period of time. In the event that the study drug does not sufficiently control the subject's acne, the Investigator, at their election, may prescribe select additional medication(s)¹² that can be taken in addition to the investigational test article. Ideally these measures should be used only for brief period(s) of time, if medically necessary, to reasonably control the subject's acne, during the study. These medications are limited to certain products (e.g., topical anti-acne cleansers, oral antibiotics, or intralesional steroid injections for cyst/nodular lesions) as detailed in the list of allowed medications or therapies above.

9. STUDY PROCEDURES

The study will consist of a Baseline Visit, follow-up visits at Months 1, 3, 6, and 9, and follow-up phone calls at Months 4.5 and 7.5. For subjects in the Phase 3 pivotal studies randomized to active (CB-03-01 cream, 1% twice daily), the total treatment period will be 12 (3+9) months; whereas for those subjects in the Phase 3 pivotal studies randomized to vehicle, the total treatment period will be 9 (0+9) months.

During the LTF study, treatment on face and/or trunk for a subject may be discontinued if/when acne is under successful control (achieves an IGA of grade 0 or "minimal" grade 1) and re-instated if/when acne worsens ($IGA \geq 2$), according to the assessment of the investigator for each respective treatment area. Subjects MUST be seen by the investigator via a scheduled or unscheduled visit to change (i.e., restart or stop) test article dosing).

Specific activities for each study visit are listed below.

9.1 Visit 4-LTF Baseline (LTF-Day 1) [Visit 4-Pivotal + 3 days]

Informed consent/assent can be obtained up to 45 days before Visit 4-LTF. *Note: Consent/assent for this extension study should not be signed at Baseline of the Phase 3 pivotal study (i.e., Visit 1).* For this LTF study, subjects must rollover from the Phase 3 pivotal study (CB-03-01/25 and CB-03-01/26) into this study AT or WITHIN THREE (3) DAYS of Visit 4-Pivotal.

¹² For US sites: OTC acne cleanser containing 2% salicylic acid or 5% benzoyl peroxide and doxycycline will be provided by the investigator. The subject will be responsible for other additional acne medications that may be prescribed by the investigator.

At this visit, the investigator or designee will:

- Obtain a signed, written informed consent (unless the subject signed a consent within the past 45 days). *Note: A subject under 18 years of age must provide written informed assent and be accompanied by the parent or legal guardian at the time of assent/consent signing. The parent or legal guardian must provide informed consent for the subject. If a subject becomes 18 years of age during the study, the subject must provide written informed consent at that time to continue study participation.*
- Confirm the subject meets the inclusion/exclusion criteria.
- Confirm demographics and medical / dermatological history were collected in the Phase 3 pivotal study (Visit 1-Pivotal).
- Review any ongoing concomitant medications and procedures.
- Perform a brief physical exam (including vital signs, height, and weight).
- Perform a UPT for all WOCBP (see [Section 5.1](#) for definition). The results must be negative for the subject to be enrolled. *Note: If Visit 4-Pivotal and Visit 4-LTF occur on the same day, the results of the UPT performed during the End of Study (EOS) visit of the Phase 3 pivotal study can be used.*
- Confirm that an IGA was performed and LSRs were assessed for the face at Visit 4-Pivotal.
- Discuss with the subject if truncal acne will be treated. If applicable, identify the truncal treatment area and record the percent BSA of the truncal treatment area (see [Section 10.3](#)). *Note: If the investigator and the subject designate a treatment area for truncal acne, the subject must continue to treat this area per protocol for the duration of the study as detailed in [Section 6.2](#).*
- Prior to the first application of the test article, for the trunk (if applicable).
 - Perform IGA (see [Section 10.1](#)); and
 - Perform LSR assessment (see [Section 10.2](#)).
- Determine if the subject requires ongoing therapy based on IGA scores of the face and trunk. *Note: If a subject's acne is totally clear (IGA=0) on face and/or trunk, the subject will not receive or apply the ITA for the first month of the study and will be reassessed at Visit 5 or earlier (after an unscheduled visit), if acne worsens (be it on the face and/or the trunk) before Visit 5.*
- Dispense the Subject Instruction Sheet to the subject and parent/guardian (if applicable) ([Appendix 1](#)), as required.
- Dispense the Subject Diary to the subject and parent/guardian (if applicable) and provide completion instructions ([Appendix 2](#)), as required.
- Weigh and dispense the test article and complete the Study Medication Accountability Log, as required ([Appendix 3](#)).
- Instruct the subject and parent/guardian (if applicable) where and how to apply the initial dose of the test article following the procedures in [Section 6.2](#). The first application should occur in the office under supervision of the study staff, except for those subjects with clear facial acne and no truncal acne.

- Record any AEs.
- Assess LSRs post-application for face AND trunk, separately, and as applicable (see [Section 10.2](#)).
- Instruct the subject and parent/guardian (if applicable) to apply the test article to the designated treatment areas (i.e., face and/or trunk) twice per day, with at least eight hours between applications.
- Remind the subject that if the subject feels that his/her acne has cleared or significantly worsened (for those subjects with IGA=0), the subject should contact the investigator for an unscheduled visit. *Note: Subjects MUST be seen by the investigator via a scheduled or an unscheduled visit to change (i.e., start or stop) test article dosing on either treatment area (face and trunk).*
- Schedule Visit 5 (LTF-Month 1).

9.2 Visit 5 (LTF-Month 1) [Day 29 \pm 10], Visit 6 (LTF-Month 3) [Day 85 \pm 15], and Visit 8 (LTF-Month 6) [Day 183 \pm 15]

At this visit, the investigator or designee will:

- Observe/query the subject about any changes in his/her health since the previous study visit, including AEs and concomitant medications/therapies, and document the findings.
- Perform a UPT for all WOCBP (see [Section 5.1](#) for definition) (**Visit 8 ONLY**).
- Perform IGA for face AND trunk, separately, and as applicable (see [Section 10.1](#)).
- Assess LSRs for face AND trunk, separately, and as applicable (see [Section 10.2](#)).
- Determine if the subject requires ongoing therapy or if treatment needs to be (re)started based on IGA scores of the face and trunk. *Note: Treatment on the face and/or trunk may be discontinued if/when acne clears (achieves an IGA of grade 0 or “minimal” grade 1) and re-instated if/when acne worsens (IGA \geq 2) according to the assessment of the investigator for each respective treatment area. Also, if a treatment area for truncal acne was not identified at Baseline (Visit 4-LTF), one may be designated at a subsequent visit (e.g., if acne worsens in the truncal area), but once treatment begins in such treatment area, the subject must continue to treat the designated area per protocol for the remainder of the study as detailed in [Section 6.2](#).*
- Review test article compliance based on Subject Diary and weights of the test article. Remind the subject to apply the test article to the designated treatment areas (i.e., face and/or trunk) twice per day, with at least eight hours between applications.
- Dispense an updated (or new) Subject Instruction Sheet to the subject and parent/guardian (if applicable) ([Appendix 1](#)), if the subject is starting treatment at this visit.
- Collect the old and dispense a new Subject Diary to the subject and parent/guardian and provide completion instructions ([Appendix 2](#)), if applicable (i.e., acne treatment on the face and/or trunk shall continue per protocol as detailed in [Section](#)

- 6.2). Any noteworthy discrepancies in the Subject Diary should be queried and documented.
- Collect all previously dispensed test article and complete the Study Medication Accountability Log ([Appendix 3](#)).
 - Weigh and dispense [only if applicable (i.e., acne treatment on the face and/or trunk shall continue per protocol)] new containers of the test article and complete the Study Medication Accountability Log ([Appendix 3](#)). *Note: For subjects that were totally clear (IGA=0) at Baseline, if their acne on the face and/or trunk remains totally clear (IGA=0), then do not dispense the test article. If treatment shall not continue per protocol as detailed in [Section 6.2](#), collect all containers of the test article. PREVIOUSLY RETURNED TEST ARTICLE SHOULD NOT BE RE-DISPENSED.*
 - If treatment is started for the first time (in this LTF study) on the face and/or trunk,
 - Discuss with the subject if truncal acne will be treated. If applicable, identify the truncal treatment area and record the percent BSA of the truncal treatment area (see [Section 10.3](#)). *Note: If the investigator and the subject designate a treatment area for truncal acne, the subject must continue to treat this area per protocol for the remainder of the study.*
 - Instruct the subject and parent/guardian (if applicable) where and how to apply the initial dose of the test article following the procedures in [Section 6.2](#). The first application should occur in the office under supervision of the study staff.
 - Record any AEs.
 - Instruct the subject and parent/guardian (if applicable) to apply the test article to the designated treatment areas (i.e., face and/or trunk) twice per day, with at least eight hours between applications.
 - Remind the subject that if the subject feels that his/her acne has cleared or significantly worsened (for those subjects with IGA=0), the subject should contact the investigator for an unscheduled visit. Acne will be managed per [Section 6.2](#) and [Section 8.2](#). *Note: Subjects MUST be seen by the investigator via a scheduled or an unscheduled visit to change (i.e., start or stop) test article dosing on either treatment area (face and trunk).*
 - Schedule follow-up visit (at Visit 5 and 6) or an end of study (EOS) visit (at Visit 8).

9.3 Visit 7: Phone Call 1 (LTF-Month 4.5) [Day 137 \pm 15] and Visit 9: Phone Call 2 (LTF-Month 7.5) [Day 228 \pm 15]

The investigator or designee will contact the subject by telephone to:

- Review any changes in his/her health, with the subject or parent/guardian (as appropriate), since the previous study visit, including AEs and concomitant medications/therapies, and document the findings.
- Review test article compliance.
- Emphasize need to maintain the Subject Diary daily with each application.

- In the event that either of the following occur prior to the next scheduled visit, the subject may be seen in the clinic as an unscheduled visit at the discretion of the investigator:
 - Improving (appears to have achieved an IGA of grade 0 or “minimal” grade 1) or worsening (IGA \geq 2 after treatment was stopped) of the subject’s acne such that the treatment may be discontinued or restarted, respectively; OR
 - A concern regarding an AE or the subject’s progress; OR
 - Other item of note from the investigator’s perspective.
- *Note: Subjects MUST be seen by the investigator via a scheduled or an unscheduled visit to change (i.e., start or stop) test article dosing on either treatment area (face and trunk).*
- In the event an in-office visit is required, the site should schedule an unscheduled visit for evaluation in a timely fashion.
- Confirm the next scheduled visit.

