
	
and subject designate a treatment area for truncal acne, the subject must continue to treat this area for the duration of the study with dosing adjustments per protocol as detailed in Section 6.2. If the investigator and subject do not designate a treatment area for truncal acne at this visit, one may be designated at subsequent visits (e.g., if acne worsens in the truncal area); however, once treatment begins in such truncal treatment area, the subject must continue to treat this area for the remainder of the study as detailed in Section 6.2. If applicable, IGA and LSRs [pre-application] for the trunk will also be assessed at this visit. Ongoing concomitant medications and procedures will be reviewed. The subject (and parent/guardian, if applicable) will be instructed on how to apply the investigational test article (ITA). ITA and subject diary will be dispensed. The first dose will be applied during this visit under supervision of the investigator, except for those subjects with clear facial acne and no truncal acne. LSRs post-application (for both face and trunk separately, as applicable) and adverse events (AEs) will be assessed. The subject will be scheduled for the first follow-up visit. NOTE: If a subject's acne is totally clear (i.e., IGA=0) on face and/or trunk, the subject will not receive or apply the ITA at home for the first month of the study and be reassessed at Visit 5 or earlier (after an unscheduled visit), if acne worsens (be it on the face and/or the trunk) before Visit 5.
 
Visits 5 (LTF Month 1), 6 (LTF Month 3), and 8 (LTF Month 6): Subjects will return to the clinic. IGA, LSRs, and AEs will also be assessed. Concomitant medications and procedures and ITA compliance will be reviewed. A UPT (if applicable) will be performed at Visit 8. Assessment of the subject's acne will be made on face and trunk to determine if the subject requires on-going therapy or if treatment needs to be started (i.e., for subjects with an IGA=0 at Baseline [Visit 4-LTF]) or restarted (after a previous discontinuation due to acne clearing). Based on this determination, ITA and a subject diary will be dispensed/returned (as required). For subjects starting treatment at this visit, the first dose of the ITA will be applied under supervision of the investigator. The subject will be scheduled for a follow-up visit (at Visit 5 and Visit 6) or end of study (EOS) visit (at Visit 8).
 
Visit 7: Phone Call 1 (LTF Month 4.5) and Visit 9: Phone Call 2 (LTF Month 7.5): The site staff will contact the subject by telephone to review any changes in concomitant medications and procedures as well as test article compliance. Site staff will query the subject about any AEs and will confirm the next appointment. In the event there is:
 
a) improving or worsening of the subject's acne such that the treatment may be discontinued or restarted, respectively, OR
 
b) a concern regarding an AE or the subject's progress based upon the Phone Call visit,
 
the subject may be seen in the clinic as an unscheduled visit at the discretion of the investigator. However, to change (i.e., restart or stop) test article dosing on either treatment area (face and/or trunk), the subject must be seen and evaluated in person by the investigator or designee.
 
Visit 10 (Month 9): End of Study (EOS) Visit & Early Termination. Subjects will return to the clinic for the final visit. UPT (if applicable) will be performed. IGA, LSRs, and AEs will be assessed. Concomitant medications

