APPENDIX 3 TEST ARTICLE INFORMATION

A 3.1 Test Article Packaging and Labeling

The test articles will be packaged and labeled by the Sponsor or designee. CB-03-01 cream, 1% will be packaged in blind-end epoxy lined aluminum tubes, with a polypropylene cap closure, containing 30 grams or 60 grams of the test article. Each subject will be assigned a subject number (carried over from Phase 3 pivotal study [CB-03-01/25 or CB-03-01/26]) and provided with sufficient test article in standard packaging for the designated treatment period during the study.

Tube Labels

Each tube will contain, at a minimum, the following information: the study/protocol number, subject identifiers (e.g., subject number [to be filled in]), the contents, the tube number (to be filled in) with test article batch number), an investigational test article disclaimer (e.g., Caution: New Drug Limited by United States law to investigational use), and the appropriate storage conditions for the test article.

A 3.2 Test Article Storage and Preparation

The test articles will be stored under secure conditions until they are dispensed to the subjects. Test articles should be stored in accordance with the tube labels.

A 3.3 Dispensing Test Article

The test article must be dispensed only to study subjects and only at study sites specified on the form FDA 1572 (or other documents required by the governing national health authority) by authorized personnel as required by applicable regulations and guidelines.

Sufficient test article will be provided to each subject as needed for the designated treatment period. For those subjects with clear facial acne and no truncal acne at Baseline (Visit 4-LTF), the test article will NOT be dispensed and the subject will be reassessed at Visit 5 or earlier (after an unscheduled visit), if acne worsens (be it on the face and/or the trunk) before Visit 5.

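### When one treatment area is clear and the other has acne at Visit 4-LTF, the synopsis and Section 9.1 notes withhold all cream, while Section 6.2 withholds it only from the clear area (minor).

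*Protocol*

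**What the plan says.** Two sets of passages govern what happens when an area is clear at Visit 4-LTF.

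- **Section 9.1, note on determining therapy:** "the subject will not receive or apply the ITA for the first month of the study". The trigger is a clear (IGA 0) face and/or trunk, and the consequence applies to the subject.
- **Synopsis, Visit 4-LTF note:** the same trigger, with the consequence "the subject will not receive or apply the ITA at home for the first month of the study". The added reference to home use is the only material difference.
- **Section 6.2, application:** "the subject will not apply the test article to the area(s) that is clear at home for the first month of the study". Here the consequence applies to the area.
- **Section 6.2, dispensing:** "If acne is totally clear on the face and the trunk has not been designated for treatment, the subject will not be dispensed" cream at that visit.
- **Appendix 3, A 3.3:** "For those subjects with clear facial acne and no truncal acne at Baseline (Visit 4-LTF), the test article will NOT be dispensed".

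Section 9.1 also has a bullet on the supervised first application. It exempts only subjects who have both a clear face and no acne on the trunk.

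For later visits, the Section 9.2 note on subjects who were totally clear at Baseline says "if their acne on the face and/or trunk remains totally clear (IGA=0), then do not dispense the test article".

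**The concern.** The notes in the synopsis and Section 9.1 stop cream for the whole subject as soon as one area is clear. Section 6.2 stops it area by area. A site following the first pair literally gives nothing to a subject with a clear face and designated truncal acne. A site following Section 6.2 treats the trunk. Section 9 is introduced as the list of activities for each visit, so a literal reading of its note is a realistic way for a site to act.

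The study exists to measure exposure and safety, and several derived quantities depend on which reading a site used:

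- **TEAE window.** Adverse event collection starts at first dose (protocol Section 14), and TEAEs are counted from first dose (SAP 7.9.2).
- **Compliance.** It is the ratio of actual to scheduled applications, evaluated at each visit and overall (SAP 7.3) and summarised separately for face and trunk (SAP 7.8.1). Neither section says what is scheduled during a hold.
- **Exposure targets.** Only subjects without material dosing non-compliance count towards the 300 subjects at 6 months and 100 at 12 months (SAP 7.2).

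**Working it through.** The plan states no figure on this point, so the main check sets the rules side by side for each combination at Visit 4-LTF.

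| Status at Visit 4-LTF | Synopsis and 9.1 notes, read literally | Section 6.2 | A 3.3 |
|---|---|---|---|
| Face clear; trunk without acne and not designated | No cream | No cream dispensed | No cream dispensed |
| Face clear; designated trunk has acne | No cream | Trunk only | Dispensing not barred |
| Face has acne; designated trunk clear | No cream | Face only | Dispensing not barred |
| Both clear; trunk designated | No cream | Nothing applied at home | No cream dispensed |

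The rules agree in rows 1 and 4 and conflict in rows 2 and 3.

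Row 2 also shows a conflict inside Section 9.1. That subject is not exempt from the supervised first application, yet the note in the same section says the subject neither receives nor applies cream. The synopsis note, limited to home use, avoids that particular clash.

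**Length of a hold.** Inputs from the Schedule of Events: Visit 5 at Day 29 ± 10, end of study at Day 274. Twice-daily use is from Sections 6.2 and 9.1.

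- Study days: 274 − 1 = 273. Applications: 273 × 2 = 546 per area.
- Hold ending at Visit 5: 29 − 1 = 28 days. Across the window, 19 − 1 = 18 to 39 − 1 = 38 days.
- Share of study days: 28/273 = 10.3%; range 18/273 = 6.6% to 38/273 = 13.9%.
- Applications held: 56; range 36 to 76.

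**Visit 5 compliance for the area with acne, if the site withheld all cream.**

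- Held applications counted as scheduled (Section 6.2 as the standard): 0/56 = 0%, or 1/56 = 1.8% if the supervised dose was given. Both are below the SAP's 80% cut-off.
- Held applications not counted (Section 9.1 as the standard): 0/0, undefined.

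**Overall compliance for that area.** Assume twice-daily treatment for the rest of the study, with no later stop for clearing.

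- Perfect use after the hold, held applications counted: (546 − 56)/546 = 89.7%; range (546 − 76)/546 = 86.1% to (546 − 36)/546 = 93.4%.
- Use after the hold needed to reach 80% overall: 0.80 × 546 = 436.8, and 436.8/490 = 89.1%.
- A subject using 85% of the later applications scores 0.85 × 490/546 = 76.3% if held days count, and 85% if they do not.

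So the choice settles the Visit 5 classification outright. It changes the overall classification only for subjects who also miss a fair number of later doses.

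**The case against.** The strongest reply is that the protocol as a whole points to area-level dosing. Stopping and restarting is left to the investigator separately for each treatment area in the synopsis and in Sections 4, 6.2, 9 and 9.2. The instruction sheet has staff circle face, trunk or both. Section 9.1 sends staff to Section 6.2 for the initial dose, and its first-application exemption fits an area-by-area reading of and/or. Taken wholly literally, the note could bar facial cream because of a clear trunk, an implausible intention in a facial acne extension. This carries weight: many sites may have read the note that way. It does not remove the conflict, because the note has no area limit and speaks of not receiving cream. Dispensing is to the subject, not to an area.

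Several stronger readings are tempting, and the documents do not support them.

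- *The hold repeats at Visits 5, 6 and 8.* The and/or in the Section 9.2 note is ambiguous in the same way, but the note covers only subjects totally clear at Baseline. The same bullet allows dispensing when treatment of either area continues.
- *Appendix 3 states an area-level rule.* A 3.3 is a dispensing rule. It conflicts with Section 9.1 on who gets cream and says nothing about which area is treated.
- *Each affected subject loses at least 28 days.* The visit window gives 18 to 38 days, and an unscheduled visit can end the hold sooner if acne worsens.
- *The number of affected subjects can be estimated.* The documents give no basis for one.
- *The SAP counts treatment from Visit 4-LTF.* No section says so. SAP 7.8.1 to 7.8.4 already list compliance by area, first and last application, treated areas, dose adjustments, and facial and truncal application times.

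It is also fair to say that the protocol correction comes late: SAP 2.5 reports 609 subjects included at 75 sites.

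**Conclusion.** The contradiction is real and stands in the current text. For a subject with one clear area and acne on the other designated area, the synopsis and Section 9.1 notes read literally give the opposite dispensing outcome from Section 6.2 and A 3.3. Section 9.1 also disagrees with its own first-application bullet. Section 9.2 is supporting evidence only.

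Severity is minor. The effect is bounded at about 7% to 14% of study days for a hold that runs to Visit 5. The number affected is unknown but probably small: truncal treatment is optional, and designating a trunk that is already clear would be unusual, which leaves mainly subjects with a clear face and designated truncal acne.

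The consequence that can still be controlled is in the analysis. Visit 5 compliance for the held area is either near zero or undefined until the denominator is specified. Any effect on the 300 and 100 targets assumes that the 80% cut-off is the test of material non-compliance, which SAP 7.2 does not state.

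**What to change.** - **Protocol:** reconcile the synopsis note and the Section 9.1 note with Section 6.2 and A 3.3, and align the Section 9.1 first-application bullet and the Section 9.2 note, so that one rule is stated throughout. Which rule is for the sponsor to decide. With enrolment reported in the SAP, this mainly serves the record and the study report.
- **SAP 7.8.2 to 7.8.4:** identify subjects with a one-area hold at Visit 4-LTF, and how each was handled, from the application dates, treated areas and dose adjustments already listed.
- **SAP 7.3:** state whether held days count as scheduled applications for that area, and how a zero denominator is reported at a visit.

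Cost: a clarification to the protocol text, one sentence in SAP 7.3 and one flag derived from existing data. No new procedures or data collection. The SAP states that it is finalised before database lock, so the SAP changes should be made by then.
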